**Protocol/SAP**

**October 6, 2018**

# Research Protocol

## Initial Visit

**Study population.** Enrollment is planned to achieve a total of 68 patients, with each subject undergoing two injections. All patients will receive 2 injections over the study time period as part of this cross-over study. Participants must be adult patients (age 18 or older) with medication-refractory non-neurogenic OAB subject to the following inclusion and exclusion criteria (Table 1). Patients who elect to proceed with intravesical BTX-A injection as third line therapy, and are deemed appropriate for treatment by the clinician, will be considered for eligibility. Patients presenting for injection will be screened and consented prior to the first injection, and this consent will apply for the duration of the study (over two injections).

**Demographic and clinical data:** Participants will complete a standardized questionnaire assessing demographics and pertinent medical history including surgical history, current and past OAB therapy, history of urinary tract infections (UTIs) and urinary retention, and self-reported diagnoses of comorbid medical conditions. We will supplement this information with abstracted data from electronic medical records on past medical and surgical history, urinalysis, urine culture data, and post-void residual.

**Note:** Recurrent UTI will be defined as three or greater culture documented UTIs within a 12 month period.

**Urinary tract infection:** At enrollment, patients will complete a medical history questionnaire which will include information related to prior UTIs. Eligible patients will provide urine specimen for analysis along with physician assessment. Diagnosis of symptomatic UTI prior to injection is to be made at the discretion of the clinician with exception of nitrite positive urinalysis. Patients with nitrite positive urine on the day of injection, regardless of symptoms, will be excluded from enrollment. Nitrite positive urinalyses will be sent for urine culture, and patients may be enrolled in the trial at a later date following treatment. On the day of injection a voided urine specimen will be obtained from all patients and sent for urine culture. This allows for assessment of the bladder milieu at the time of injection, however will not be used for treatment purposes unless patient subsequently becomes symptomatic. Post-void residual will be obtained, per standard clinic protocol, for all patients receiving treatment. This will be done with bladder scanner in clinic and with catheterized specimen for patients receiving an injection in the operating room if PVR not previously recorded in the medical record within 8 weeks prior to injection.

**Assessment of overactive bladder:** Participants will complete baseline standardized, validated questionnaires documenting urinary symptoms and quality of life. Instruments will include the American Urologic Association Symptom Index (AUA-SI), Overactive Bladder Questionnaire short-form (OABq-SF), Patient Perception of Bladder Control questionnaire (PPBC) and the Patient's Global Impression of Improvement (PGII).

**Inclusion/exclusion criteria.** Study criteria are listed in the Table. A diagnosis of OAB and the decision to proceed to third line treatment will be determined by clinician according to AUA guidelines.

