### Day of Injection

#### **New Patients:**

New patients will undergo complete history and focused physical exam. PVR will be obtained at initial clinic visit. If PVR has not performed or is not on file on the day of injection, PVR will be obtained prior to injection. If PVR >250cc, it will be repeated after double void. If again greater than >250cc, patient will be excluded from enrollment for that injection. Physician will be responsible for determining if patient has symptomatic UTI on the day of injection, and exclude the patient if appropriate (UA will be utilized in making this decision).

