### 2nd Injection:

Patients will have been consented at the beginning of the study to include both 1st and second injections and therefore do not need to be re-consented. The exact protocol is followed as stated above, however, patients will receive the treatment from the arm NOT received after the first injection. For example, patients who received extended 3 day course of antibiotics after the first injection, will receive only peri-procedural antibiotics after the 2nd injection.

The timing of the second injection will be determined by the clinician and patient based on symptoms and will not be standardized.

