### Statistical analysis plan

The primary endpoint is the presence (Yes/No) of urinary tract infection 3 weeks post procedure. We will estimate the probability of urinary tract infection for both treatment groups. Baseline patient-characteristics data will be collected and tabulated. The trial design (crossover) will guarantee that the baseline covariates will be distributed similarly for both treatment groups. Carryover effect is minimized since the time between the first and second injections is sufficiently long for any residual treatment effect from the first period to wear off. For each treatment, the probability of UTI will be estimated and presented with 95% Wilson confidence intervals. We aim to establish non-inferiority of EDA to PPA with the non-inferiority margin of 10 percentage points. We will estimate the proportion of patients who will have infection with EDA but not with PPA.

Sample size and power were computed using the method described in Chow et al . To compute the sample size, we need to specify, in addition to the usual parameters (type I error rate of 5%, type II error rate of 10%, non-inferiority margin of 0.10, and difference under the alternative of 0), the variance of difference, which takes value of 1 if only EDA is successful, -1 if only PPA is successful, and 0 if EDA and PPA yield the same outcome. This variance, in turn, depends on the true probability of infection with EDA and PPA and also concordance of the result (success/failure) within a given patient. Under a pessimistic scenario where P[infection] is 25% and 35%, and the concordance is weak (Knowing the result of other treatment only changes the probability by 5 percentage points for the patient), the variance is 0.40, and the corresponding sample size is 68. Even if the true P[infection] is 35% and 45%, we will maintain the excellent power as shown below in the Table.

Power with n=68

P[infection] with EDA	0.25	0.25	0.35	0.35
P[infection] with PPA	0.35	0.35	0.45	0.45
Concordance	+0.05	+0.10	+0.05	+0.10
Power	90%	92%	83%	86%

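### The power table counts 68 complete pairs and 68 is also the total enrolment, with no allowance for missing second outcomes; the base power must be corrected first

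*Combined protocol and SAP*

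**What the plan says.** Under Study population in the Initial Visit section: "Enrollment is planned to achieve a total of 68 patients, with each subject undergoing two injections". The next sentence says that all patients will receive two injections.

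The Statistical analysis plan bases the sample size on a within-patient difference that "takes value of 1 if only EDA is successful, -1 if only PPA is successful", and is 0 when the two outcomes agree. Its parameters are "type I error rate of 5%, type II error rate of 10%, non-inferiority margin of 0.10, and difference under the alternative of 0". It concludes that "the variance is 0.40, and the corresponding sample size is 68". The table beneath gives power of 90%, 92%, 83% and 86% at n=68.

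On the second injection, the 2nd Injection section says: "The timing of the second injection will be determined by the clinician and patient based on symptoms and will not be standardized". It sets no latest date, and it says that the protocol described earlier applies again. That protocol includes the residual-urine rule in the New Patients section, under which, after a repeated high value, the "patient will be excluded from enrollment for that injection". For established patients, eligibility is decided by the provider from urinalysis and residual urine.

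Nowhere is there an expected loss rate, a replacement rule, or a statement of how a patient with one injection enters the primary analysis.

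**The concern.** The unit that was powered is the pair: one patient with an infection outcome after each injection. The plan uses one number, 68, both for pairs in the power table and for patients enrolled. Any patient who has no second injection, or no outcome after it, removes a pair. The plan's own procedures leave room for this, because the second injection follows symptoms and choice and comes after repeat screening.

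What is at stake is how the result is read. If a non-inferiority trial misses its margin, readers need to know whether it had a real chance of meeting it. A power figure that ignores loss, and that does not follow from its stated inputs in any case, gives them the wrong answer.

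**Working it through.** **Inputs, all from the Statistical analysis plan unless noted.** Type I error 5% (sidedness not stated; taken as one-sided), power 90%, margin 0.10, true difference 0, variance 0.40, n = 68. Enrolment of 68 is from the Initial Visit section. Loss rates are assumptions, because the documents give none.

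**1. The figure 0.40.** The first scenario reads: "Under a pessimistic scenario where P[infection] is 25% and 35%, and the concordance is weak", with concordance +0.05. Take concordance to mean that an infection under one treatment raises the probability under the other by 0.05. Then P(both) = 0.25 × (0.35 + 0.05) = 0.10, and P(outcomes differ) = 0.25 + 0.35 − 2 × 0.10 = 0.40. This reproduces 0.40 as a variance, as the plan calls it (0.39 if the squared difference of 0.10² is subtracted).

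**2. The sample size.** For a paired non-inferiority comparison, n = (z_α + z_β)² × Var / (margin − difference)².

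n = (1.645 + 1.282)² × 0.40 / 0.10² = 8.564 × 40 = 342.6, so 343 pairs. The stated 68 is not reproduced. A two-sided 5% gives 421.

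**3. Power at 68 complete pairs.** Power = Φ(0.10 × √(n/0.40) − 1.645). At n = 68 this is Φ(1.304 − 1.645) = Φ(−0.341) = 0.367. Across the four tabulated scenarios, still with difference 0, the range is 34% to 38%.

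**4. Where 68 and 90% may come from.** They are approached if 0.40 is entered as a standard deviation and the answer is read as patients per sequence: 8.564 × 0.16 / (2 × 0.01) = 68.5. Power is then Φ(0.10 × √(2 × 68)/0.40 − 1.645) = Φ(2.915 − 1.645) = 0.898. The same route gives about 90%, 93%, 83% and 88% for the four columns, against the stated 90%, 92%, 83% and 86%. This is a reconstruction, because the plan prints no formula. It would need about 137 pairs in total.

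**5. Adding loss.** 68 × 0.9 = 61.2, 68 × 0.8 = 54.4, 68 × 0.7 = 47.6 and 68 × 0.6 = 40.8, rounded to whole pairs. The columns are:
- A: stated inputs, Φ(0.10 × √(n/0.40) − 1.645).
- B: 0.40 treated as a standard deviation, but with n as actual pairs, Φ(0.10 × √n/0.40 − 1.645).
- C: variance 0.40, with EDA truly 10 points better as in the table's scenarios, so the distance to the margin is 0.20: Φ(0.20 × √(n/0.40) − 1.645).

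| Assumed loss | Pairs | A | B | C |
|---|---|---|---|---|
| 0% | 68 | 37% | 66% | 83% |
| 10% | 61 | 34% | 62% | 80% |
| 20% | 54 | 31% | 58% | 75% |
| 30% | 48 | 29% | 53% | 71% |
| 40% | 41 | 26% | 48% | 65% |

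Column A uses the inputs the plan states. Column C contradicts the stated difference of 0 and still does not reach 90% with no loss: it needs 8.564 × 0.40 / 0.04 = 85.6, so 86 pairs.

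**The case against.** The plan says that all patients will receive two injections, and the enrolment sentence can be read as a target of 68 completers. The 2nd Injection section leaves the timing open; it does not call the injection optional. The residual-urine rule stands under New Patients, and exclusion for one injection may only defer it, much as patients with nitrite-positive urine may be enrolled later after treatment. The references in the follow-up sections to patients receiving multiple injections are weak evidence, because an inter-injection time needs two injections by definition.

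This stands to the extent that loss is possible, not certain, and its size is unknown. It does not remove the point. Reaching 68 completers would need continued enrolment or replacement, and the plan describes neither.

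A reader might draw three stronger conclusions, and the documents support none of them:
- **That the stated power is right if nobody is lost.** At 68 complete pairs the stated inputs give about 37%, so the 90% fails before any loss.
- **That loss takes power from 90% to 87%, 83%, 79% and 73%.** That series comes from Φ(0.10 × √(2n)/0.40 − 1.645) at n = 61, 54, 48 and 41. It is the reconstruction in step 4 of the working, and the powers belong to 122, 108, 96 and 82 pairs, not to the pairs this trial would have.
- **That the trial will certainly lose pairs.** The plan's rules allow it; they do not establish it.

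**Conclusion.** The point holds as a missing allowance, secondary to a larger error in the base calculation. The power table is for 68 patients with outcomes after both injections, 68 is also the whole enrolment, and nothing covers a missing second outcome.

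On the stated inputs, losses of 10% to 40% cost about 3 to 10 percentage points (37% down to between 34% and 26%). The gap from 90% to 37% exists without any loss. These figures assume one-sided 5%, a normal approximation, a variance of 0.40, a true difference of 0 and an analysis of complete pairs only. At two-sided 5%, 68 pairs give about 26%: Φ(1.304 − 1.960). Adding a loss allowance to 68 would not repair the plan, because 68 is not the number that its inputs produce.

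**What to change.** In this order:

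1. Redo the base power calculation. State the formula, the sidedness, whether 0.40 is a variance or a standard deviation, whether n is total or per sequence, and whether the true difference is 0 or the 10 points in the table.
2. Restate power by number of completed pairs, for example 68, 61, 54 and 48, and say that 68 is the enrolment. If the reconstructed series is shown at all, label it as a reconstruction.
3. Specify a primary analysis that uses one-injection patients as well as pairs, for example a GEE or mixed model for the risk difference with treatment and period. State its missing-data assumption, since symptoms influence who returns and when.

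The cost is a less favourable stated power, revised SAP wording and some extra analysis work. No extra patients are needed for this change. Whether the corrected power is acceptable is a separate decision for the sponsor.

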**Table 1. Criteria for study participation.**

Inclusion criteria	Exclusion criteria

• ≥ 18 years of age

	

• Post void residual urine >250ml on two occasions

• Medication refractory OAB, identified per AUA guidelines

	

• Untreated, symptomatic UTI

• Comorbid neurological conditions, including spinal cord injury, systemic neurologic illnesses (i.e. multiple sclerosis, Parkinson's disease) or central nervous system disease (i.e. brain tumor, stroke)

• Prior pelvic irradiation

• Current or prior bladder malignancy

• Hematuria lacking a clinically appropriate evaluation

• Chronic catheterization or SIC

--	--

### Day of Injection

#### **New Patients:**

New patients will undergo complete history and focused physical exam. PVR will be obtained at initial clinic visit. If PVR has not performed or is not on file on the day of injection, PVR will be obtained prior to injection. If PVR >250cc, it will be repeated after double void. If again greater than >250cc, patient will be excluded from enrollment for that injection. Physician will be responsible for determining if patient has symptomatic UTI on the day of injection, and exclude the patient if appropriate (UA will be utilized in making this decision).

#### **Established patients:**

Established patients continuing injection will be screened and consented on the day of presentation for injection. PVR within 8 weeks must be documented in chart. If no PVR documented within 8 weeks, must repeat PVR prior to injection with either a bladder scanner or catheterized value. UA obtained per existing clinic policy. Eligibility determined by provider based on UA and PVR.

Demographic information including comorbidities will be abstracted from patients' electronic medical records, and a focused history and physical will be performed on day of injection.

**Injection protocol:** All patients will undergo injection per a standardized protocol of 1ml injection per site at a concentration of 10 units/ml. For patients undergoing injection in the clinic setting, an intravesical instillation of diluted local anesthetic will be used prior to injection, if no allergy to anesthetic is reported. For those performed in the operating room, anesthesia will be administered per the discretion of anesthesiology team. The number of units injected will be documented and accounted for during analysis by stratifying patients according to the amount of BTX-A injected.

**Antibiotic protocol:** On the day of injection patients will be randomized to either the experimental or control arm according to a computer generated randomization scheme (see explanation of randomization below). Patients randomized to the experimental arm will receive a single dose of trimethoprim/sulfamethoxazole (800/160mg) peri-procedurally. Patients randomized to the control arm will receive one dose of trimethoprim/sulfamethoxazole peri-procedurally and additionally be prescribed trimethoprim/sulfamethoxazole twice daily for three days. Patients who are allergic will receive amoxicillin/clavulanic acid (875/125mg) twice daily for three days. If allergic to both of the above antibiotics, patients will receive 100mg nitrofurantoin BID for three days. Our budget reflects published data regarding our local antibiogram and population estimates for antibiotic allergies.

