### 3-week Post-Procedure Visit:

#### All patients at 3-week post-procedure visit will receive:

- a. AUA-SI, PPBC, OABq-SF, PPBC (per standard clinical practice)
- b. PVR (per standard clinical practice)
- c. UA (per standard clinical practice)
- d. Urine culture if determined necessary by physician (per standard clinical practice)

e. Post-Botox 3-Week Post Procedure Survey

**Symptoms Assessment:** Participants will complete standardized, validated questionnaires documenting urinary symptoms and quality of life for comparison. Instruments will include the American Urologic Association Symptom Index (AUA-SI), Overactive Bladder Questionnaire short-form (OABq-SF), Patient Perception of Bladder Control questionnaire (PPBC) and the Patient's Global Impression of Improvement (PGII).

**Urinary tract infection:** Patients will be assessed at a 3-week follow up visit with urinalysis. If a patient reports symptoms concerning for UTI, urine culture and antibiotic treatment will be ordered at the discretion of the clinician. All patients will be provided with instructions for reporting adverse events including clinic nurse contact information should symptoms of UTI develop. Given that our institution is a tertiary referral center and patients may report to local providers, a system will be in place to obtain all outside urine culture and antibiotic records for analysis.

**Note:** For the purposes of this study, UTI will be defined as  $\geq 10^5$  bacterial colonies in the presence of symptoms.

**Treatment success:** Patients will be assessed at post-procedure appointments at 3 weeks and a phone call at 3 months. Follow up visit will consist of urinalysis, ultrasound PVR, patient-reported questionnaires, and recording of adverse events. Efficacy of injection will be assessed via inter-injection times for patients receiving multiple injections and will be followed for the duration of the study period.

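### Intake of the three-day take-home course, which is the whole contrast in non-allergic patients, is not described as recorded or analysed, so untaken courses would shrink the comparison unseen

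*Combined protocol and SAP*

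**What the plan says.** The Antibiotic protocol (Day of Injection) defines the single-dose regimen, PPA, as the experimental arm: "Patients randomized to the experimental arm will receive a single dose of trimethoprim/sulfamethoxazole (800/160mg) peri-procedurally". The control arm, EDA, gets the same peri-procedural dose, and those patients are to "additionally be prescribed trimethoprim/sulfamethoxazole twice daily for three days". Each patient receives both regimens, one per injection, in randomised order.

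For allergic patients the same paragraph says: "Patients who are allergic will receive amoxicillin/clavulanic acid (875/125mg) twice daily for three days". A third antibiotic, also for three days, is named for those allergic to both. Neither sentence says which arm it applies to, and neither mentions a peri-procedural dose.

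The 3-week visit lists questionnaires, residual urine, urinalysis, culture if needed, and a "Post-Botox 3-Week Post Procedure Survey". The 3-month call lists a similar survey. The items of these two surveys are not given. The 3-week section also provides for obtaining culture and antibiotic records from outside providers, and the 3-month section asks about UTIs and how they were treated. Neither is described as recording intake of the assigned course.

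The Statistical analysis plan states: "We aim to establish non-inferiority of EDA to PPA with the non-inferiority margin of 10 percentage points". It defines no analysis population, whether as-randomised or per-protocol.

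**The concern.** In non-allergic patients the regimens are separated only by 2 × 3 = 6 doses that the patient takes at home, and the protocol describes only their prescription. A patient who takes none of them has received PPA but is counted under EDA. In a crossover, both of that patient's periods are then effectively the same regimen, and the pair says almost nothing about the contrast.

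If the trial reports that the regimens are similar, the reader will want to know whether the longer course adds little or whether it was often not taken. Without a record of intake the data cannot separate these explanations, and intake is hard to reconstruct later. What the dilution does to the formal test depends on which regimen is being tested against which, and the documents do not agree on that.

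**Working it through.** **Inputs.** From the Statistical analysis plan: "type I error rate of 5%, type II error rate of 10%, non-inferiority margin of 0.10, and difference under the alternative of 0"; infection rates of 25% (EDA) and 35% (PPA); "the variance is 0.40, and the corresponding sample size is 68". Assumed, because the documents do not give them: a one-sided 5% test (sidedness is not stated), adherence *a* between 100% and 50%, and an untaken EDA course carrying the PPA risk.

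**The plan's own figure.** The variance reproduces. If the 5-point concordance is read as a change in conditional probability, 0.25 × 0.75 + 0.35 × 0.65 − 2 × (0.25 × 0.75 × 0.05) = 0.396, or about 0.40. The sample size does not. For a paired comparison N = (z₀.₉₅ + z₀.₉₀)² × variance / margin² = 8.564 × 0.40 / 0.01 = 343 patients. A value near 68 returns only if 0.40 is entered as a standard deviation and the result is read per sequence: 8.564 × 0.40² / (2 × 0.01) = 68.5. That is a separate and larger problem. Here I keep 68 patients and variance 0.40, as the plan states them.

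**Dilution.**
- Mean EDA rate = *a* × 25% + (1 − *a*) × 35%.
- Mean PPA − EDA gap, *d* = 10 × *a* points, so each 10% of courses not taken removes 1 point.
- Standard error = √(0.40 / 68) = 0.0767.

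**Chance of declaring non-inferiority.**
- PPA tested against EDA: Φ((0.10 − *d*) / 0.0767 − 1.645). The true gap sits at the margin, so every such claim is false.
- EDA tested against PPA, as the SAP words it: Φ((0.10 + *d*) / 0.0767 − 1.645). EDA is truly better here, so the claim is correct.

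| Adherence (assumed) | Mean gap, points | PPA against EDA: false claim | EDA against PPA: success |
|---|---|---|---|
| 100% | 10 | 5.0% | 83% |
| 90% | 9 | 6.5% | 80% |
| 80% | 8 | 8.3% | 76% |
| 70% | 7 | 10.5% | 72% |
| 50% | 5 | 16.0% | 62% |

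Worked row at 80%: (0.10 − 0.08) / 0.0767 − 1.645 = −1.384, giving 8.3%; (0.10 + 0.08) / 0.0767 − 1.645 = 0.702, giving 76%.

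Simulation of the paired outcomes gave 5.3, 6.7, 8.6, 10.9 and 16.3% for the false claim, and 84, 80, 76, 71 and 61% for success. A larger trial makes the false-claim inflation worse: with 343 patients it is 14.5% at 80% adherence.

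**The case against.** **Direction.** A reader might infer that non-adherence always favours a non-inferiority claim. The documents do not support that. It favours the claim only when the tested regimen is truly worse. The SAP words the aim as EDA against PPA and assumes EDA has the lower infection rate, and on those terms dilution works against success (last column of the table). This objection stands. It does not remove the concern, because the arm labels make PPA the tested regimen. Even under the SAP's wording, if EDA were truly worse by the margin, dilution would raise the false-claim rate in the same way.

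**Surveys.** A reader might infer that nothing in the trial checks intake. That cannot be shown, since the items of the two post-procedure surveys are not in the documents and could include it. What can be said is that no check is described.

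**Allergic patients.** The six-dose contrast cannot be extended to them. As written, they receive a three-day course whichever arm they are in, so there may be no contrast in that group.

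**Size.** A reader might also reason that a true 12-point gap falls inside the margin once about 17% of courses are untaken, since 12 × (1 − 0.167) = 10. That compares an average difference with the margin, whereas a non-inferiority claim ordinarily rests on a confidence bound. With a standard error of 7.7 points the observed gap would have to be below 10 − 1.645 × 7.67 = −2.6 points. For a true 12-point gap the false-claim rate is about 2.8% at full adherence, 5% at 17% untaken and 10% at 40% untaken: a gradual rise with no threshold. Courses taken in part would dilute less.

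**Estimand.** Comparing what is prescribed, as randomised, is a legitimate question. A completers-only set selects on behaviour after randomisation, and side effects or early symptoms could influence completion, so it can be biased either way. This stands. It is why the per-protocol analysis should be supportive and should not be a second hurdle that must be passed.

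**Conclusion.** The point holds in a limited form. In non-allergic patients the contrast is a six-dose take-home course, no record of its intake is described, and no adherence-based analysis is planned. Untaken courses shrink any true difference.

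If PPA is tested against EDA, the false non-inferiority rate at a true 10-point gap rises from 5% to about 6.5%, 8% and 16% at 90%, 80% and 50% adherence. If EDA is tested against PPA with the SAP's rates, the chance of success falls from 83% to 76% at 80% adherence. The sign of the effect is therefore open until the Antibiotic protocol and the Statistical analysis plan agree on the direction of the test.

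These sizes rest on 68 patients, variance 0.40, a one-sided 5% test, and untaken courses behaving exactly as PPA. Actual adherence is unknown and may be high for so short a course. It is worth acting on because the remedy is cheap and the information is hard to recover afterwards.

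**What to change.** 1. Make sure the existing 3-week survey, after each injection, records how many doses of the assigned antibiotic were taken. If it already does, say so in the protocol.
2. In the Statistical analysis plan, pre-specify an as-randomised paired analysis and a supportive per-protocol paired analysis, limited to patients who completed the EDA course and took no extra study doses in the PPA period. Report both, and interpret any non-inferiority claim in light of whether they are consistent.
3. Reconcile the arm labels in the Antibiotic protocol with the direction of non-inferiority in the Statistical analysis plan.
4. Reconcile the allergic-patient text with the two-arm design, so that it is clear what contrast, if any, those patients contribute.

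The cost is at most one survey item, one added analysis and some clarified wording; no visit is added. The limits are that adherence is self-reported and that the per-protocol set is smaller and selected after randomisation.
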